3 LIST OF ABBREVIATIONS AND DEFINITION OF TERMS

The following abbreviations are used in this study protocol.

Abbreviation	Definition
ACR CRISS	American College of Rheumatology Composite Response Index in Diffuse Systemic Sclerosis
AEs	Adverse events
AESI	Adverse event of special interest
ALP	Alkaline phosphatase
ALT	Alanine aminotransferase
AR	Autoregressive
AST	Aspartate aminotransferase
ATC	Anatomical Therapeutic Chemical
ATS/ERS	American Thoracic Society/European Respiratory Society
BCRP	Breast cancer resistance protein
BID	Two times a day
BLM	Bleomycin
cAMP	Cyclic adenosine 3',5'-monophosphate
CFR	Code of Federal Regulations
CHMP	Committee for Medicinal Products for Human Use
CI	Confidence intervals
COVID-19	Coronavirus Disease 2019
[REDACTED]	[REDACTED]
CRF	Case Report Form
CRISS	Composite response index in diffuse systemic sclerosis
[REDACTED]	[REDACTED]
CSR	Clinical study report
CYP	Cytochrome P450
dcSSc	diffuse cutaneous systemic sclerosis
[REDACTED]	[REDACTED]
DMARDs	Disease-modifying anti-rheumatic drugs
DNA	Deoxyribonucleic acid
ECG	electrocardiogram
eCRF	Electronic case report form
eGFR	Estimated glomerular filtration rate
EOS	End of study
EOT	End of treatment
EPP	erythropoietic protoporphyrinia

Abbreviation	Definition
[REDACTED]	[REDACTED]
ET	Early termination
ESR	erythrocyte sedimentation rate
EULAR	European League Against Rheumatism
EUSTAR	European League Scleroderma Trials and Research
FDA	Food and Drug Administration
FVC	Forced vital capacity
GCP	Good Clinical Practice
GGT	Gamma glutamyl transpeptidase
GMP	Good Manufacturing Practice
HAQ-DI	Health Assessment Questionnaire Disability Index
HCV	Hepatitis C virus
HIV	Human immunodeficiency virus
HRCT	High resolution chest tomography
IB	Investigator's Brochure
ICF	Informed consent form
ICH	The International Council for Harmonisation of Technical Requirements for Pharmaceuticals for Human Use
iDMC	Independent data monitoring committee
IEC	Independent ethics committee
ILD	Interstitial lung disease
IRB	Institutional Review Board
ITT	Intent-to-treat
IWRS	Interactive Web-based Response System
KL-6	Krebs von den Lungen-6
LFT	Liver function test
MAD	Maximum Ascending Dose
MC1R	Melanocortin-1 receptor
MedDRA	Medical Dictionary for Regulatory Activities
MMRM	Mixed-effect model for repeated measures
mRSS	modified Rodnan Skin Score
MTDA	Mitsubishi Tanabe Pharma Development America
OATP	Organic anion transporting polypeptide
PAH	Pulmonary arterial hypertension
PD	Pharmacodynamic
PFT	Pulmonary function test
%pFVC	Percent predicted forced vital capacity

Abbreviation	Definition
[REDACTED]	[REDACTED]
[REDACTED]	[REDACTED]
P-gp	p-Glycoprotein
PGx	Pharmacogenomics
PhGA	Physician Global Assessment
PtGA	Patient Global Assessment
PK	Pharmacokinetic(s)
p.o.	Oral administration
PPS	Per-protocol set
[REDACTED]	[REDACTED]
PROs	patient-reported outcomes
PT	Preferred term
QD	Every day
QTc	Corrected QT interval
QTcB	Corrected QT interval using Bazett's formula
QTcF	Corrected QT interval using Frederica's formula
SAE	Serious adverse event
SAP	Statistical analysis plan
SD	Standard deviation
SHAQ	Scleroderma Health Assessment Questionnaire
SNP	single-nucleotide polymorphisms
SOC	system organ class
SP-D	Surfactant protein-D
SSc	Systemic sclerosis
SSc-ILD	Systemic sclerosis- interstitial lung disease
SUSAR	Suspected unexpected serious adverse reaction
TEAE	Treatment-emergent adverse event
[REDACTED]	[REDACTED]
[REDACTED]	[REDACTED]
ULN	Upper limit of normal
US	United States
UV	Ultraviolet
VAS	Visual Analog Scale
WHO	World Health Organization
WMA	World Medical Association
α -SMA	α smooth muscle actin

Abbreviation	Definition
XLP	X-linked protoporphryia

6 INTRODUCTION

MT-7117 (dersimelagon) is a novel orally-administered, small molecule, which acts as an agonist of melanocortin-1 receptor (MC1R) and is being developed by Mitsubishi Tanabe Pharma to reduce active inflammatory and fibrotic processes in adults with diffuse cutaneous systemic sclerosis (dcSSc).

MC1R is a member of the G-protein-coupled receptors superfamily. It is the predominant melanocortin receptor expressed in cutaneous and hair follicle melanocytes. MC1R is activated by α -melanocyte-stimulating hormone which can be locally synthesized in response to sunlight exposure. MC1R regulates the amount and type of pigment production and is a major determinant of skin phenotype and sensitivity to ultraviolet light induced damage.¹ MC1R has also been reported to be expressed by a variety of cell types, including fibroblasts, endothelial cells, and immune cells.² Activation of MC1R enhances deoxyribonucleic acid (DNA) repair, upregulates antioxidant enzymes, and reduces production of proinflammatory cytokines,³ suggesting that MC1R is important for the resolution of inflammation.⁴ Therefore, agonism of MC1R is associated not only with increased skin pigmentation, but also with regulation of inflammatory responses.^{1,4,5}

Systemic sclerosis (SSc) is a complex polygenic, autoimmune, and chronic medical condition characterized by excessive production of collagen (fibrosis), microvascular damage in the skin, joints, lung, esophagus, gastrointestinal tract, kidneys, heart, and other internal organs⁶, with an estimated prevalence in the United States (US) of 276-300 cases per million with an incidence of about 20 cases per million per year.^{7,8} The 10-year survival has reportedly improved from the 1970s (54%–60%) to the 1990s (66%–78%).⁸

The patient population is highly heterogeneous, with each patient presenting with unique combinations of organ involvement, symptoms, and progression. There are 2 major recognized patterns that the illness can take: diffuse or limited disease. In diffuse scleroderma, skin thickening occurs more rapidly and involves more skin areas than in limited disease. In addition, subjects with diffuse sclerosis have a higher risk of developing “sclerosis” (fibrous hardening) of the internal organs.⁶

The process of skin fibrosis in dcSSc is highly variable; for most subjects it includes an inflammatory phase eliciting fibrosis followed by a plateau (and slight reversal), representing established fibrosis without the presence of inflammatory signals.⁹ Skin fibrosis is measured clinically by the modified Rodnan skin score (mRSS) score,^{10,11} a subjective measure of skin thickness done by pinching/palpating the skin of the patient.

Systemic sclerosis-interstitial lung disease (SSc-ILD), the major systemic morbidity of the disease, is seen in about 30% to 40% of SSc subjects and lung fibrosis is the leading cause of death among SSc subjects, particularly in dcSSc.^{12,13} Forced vital capacity (FVC) is a clinical correlate of lung fibrosis and has the greatest decrease during the early years of disease, although it continues to decrease over the course of disease as fibrosis increases.¹² FVC decline is greater in subjects exhibiting more severe fibrosis by high resolution chest tomography (HRCT).

SSc is an extremely difficult disorder to diagnose and manage, with unknown origin or genetic predisposition. Apart from nintedanib, there are currently no treatments indicated for SSc.

Despite some recent sets of general treatment guidelines there is,^{25,41} as yet, not a defined treatment paradigm. Treatment is dependent on subtype (diffuse or limited), stage, and organ systems involved. It is believed from experts and from the literature that the reversal of established fibrosis is a difficult. Therefore, current therapeutic efforts are focused on limiting inflammation or oxidative stress in the early phase of dcSSc in order to modulate collagen overproduction and thereby prevent progression of fibrosis and controlling related symptoms. Patients receive different regimens of steroids, immunosuppressants, and anti-fibrotics. Many current treatments are minimally effective, along with carrying potentially significant safety issues, such as immune suppression.

There are numerous products in the development pipeline which target symptomatic and disease improvement in lung, skin, or both. Many of these products were initially launched for treatment of other indications (such as asthma or idiopathic pulmonary fibrosis) and are now pursued for a label extension in dcSSc. Multiple drugs in the pipeline have been discontinued due to safety and efficacy issues as well as inability to recruit clinical studies.

Mitsubishi Tanabe Pharma Development America (MTDA) is developing MT-7117 for the treatment of dcSSc. Since MT-7117 is an investigational medication, and its safety profile in humans has not yet been fully investigated, all subjects receiving MT-7117 will be closely monitored. Further information can be found in the MT-7117 Investigator's Brochure (IB).^{14,40}

6.1 Nonclinical Studies

Results of the completed nonclinical studies conducted with MT-7117, including pharmacology, pharmacokinetics (PKs), and toxicology studies, can be found in the IB.^{14,40}

6.2 Clinical Studies

Results of the completed clinical studies conducted with MT-7117 so far, and the information of ongoing or planned studies with MT-7117 can be found in the IB.^{14,40}

7 STUDY OBJECTIVES AND ENDPOINTS

7.1 Study Objectives

7.1.1. Primary Objective

To evaluate the efficacy of MT-7117 treatment in subjects with dcSSc using the American College of Rheumatology Composite Response Index in Diffuse Systemic Sclerosis (ACR CRISS) at Week 52.

7.1.2. Secondary Objectives

- To evaluate the efficacy of MT-7117 treatment for up to 52 weeks using patient-reported outcomes (PROs) as measured by the Health Assessment Questionnaire Disability Index (HAQ-DI) and Patient Global Assessment.
- To evaluate the efficacy of MT-7117 treatment for up to 52 weeks on pulmonary function as measured by percent predicted forced vital capacity (%pFVC).
- To evaluate the efficacy of MT-7117 treatment for up to 52 weeks using the Physician Global Assessment.
- To evaluate the efficacy of MT-7117 treatment for up to 52 weeks using the mRSS.
- To evaluate ACR CRISS at Weeks 16, 26, and 39.
- To evaluate ACR CRISS Score improvement proportion up to 52 weeks.

7.1.3. Exploratory Objectives

A high-contrast, black and white image showing a dark background with several bright, horizontal white bars of varying lengths. The bars are positioned at different heights and widths, creating a minimalist abstract pattern. The image is framed by a thick black border.

7.1.4. Safety Objectives

- To evaluate the safety and tolerability of MT-7117 treatment for up to 56 weeks in subjects with dcSSc.

7.1.5. Pharmacokinetics Objective

- To determine the pharmacokinetic (PK) profile of MT-7117 in subjects with dcSSc.

7.2 Study Endpoints

7.2.1 Primary Endpoint

- The ACR CRISS composite score (0-1) at Week 52.

7.2.2 Secondary Endpoint(s)

- Change in HAQ-DI from baseline at Weeks 16, 26, 39, and 52.
- Change in Patient Global Assessment from baseline at Weeks 16, 26, 39, and 52.
- Change in %pFVC from baseline at Weeks 16, 26, 39, and 52.
- Change in Physician Global Assessment from baseline at Weeks 16, 26, 39, and 52.
- Change in mRSS from baseline at Weeks 16, 26, 39, and 52.
- ACR CRISS Score at Weeks 16, 26, and 39.
- ACR CRISS Score improvement at Weeks 16, 26, 39 and 52: Proportion of subjects with $\geq 25\%$ improvement in mRSS, HAQ-DI, Patient Global Assessment, Physician Global Assessment, or $\geq 5\%$ improvement in FVC for at least 3 of the 5 ACR CRISS measures.
- ACR CRISS score responder (CRISS ≥ 0.6) at Weeks 16, 26, 39, and 52.

7.2.3 Exploratory Endpoint(s)

1

7.2.4 Safety Endpoint(s)

- Treatment-emergent adverse events ([TEAEs] including serious adverse events [SAEs], adverse events (AEs) leading to withdrawal, and adverse events of special interest [AESIs]).
- Physical examination.
- Vital signs (blood pressure, pulse rate, respiratory rate, and body temperature).
- Clinical laboratory examinations (hematology, coagulation, biochemistry, and urinalysis), including liver function markers (ALT, AST, gamma glutamyl transpeptidase [GGT], ALP, direct and total bilirubin).
- 12-lead electrocardiogram (ECG).
- Nevi (Melanocytic Lesions) appearance (assessed by a dermatologist or other qualified site staff). Any Nevi (Melanocytic Lesions) undergoing change of clinical concern during active treatment will be biopsied for follow-up and evaluated by a central pathology laboratory.

7.2.5 Pharmacokinetics Endpoint

- Assessment of plasma PK concentrations of MT-7117 measured at scheduled visits

8 STUDY DESIGN

8.1 Overall Study Design

This is a Phase 2, multicenter, randomized, double-blind, placebo-controlled, parallel-group study to evaluate efficacy, safety, and tolerability of MT-7117 in subjects with dcSSc.

The duration of the study is approximately 60 weeks; screening period up to 4 weeks, double-blind treatment period of 52 weeks, and a safety follow-up period of 4 weeks after last dose.

Following completion of the all screening assessments, subjects will return to the clinical site for start of the double-blind treatment period (Visit 2, Day 1) and baseline assessments will be evaluated and confirmed the eligibility (e.g., safety assessments, ACR CRISS components, and nevi (Melanocytic Lesions) evaluation, if nevi (Melanocytic Lesions) are present (Table 1)

Eligible subjects will be randomized in a 1:1 ratio to either MT-7117 at starting of 300 mg every day (QD) or matching placebo in a double-blind manner, [REDACTED]

Study drug will be administered once daily orally in the morning with or without food.

During the double-blind treatment period, subjects will return to the clinical site and assessments will be collected as described in Table 1.

The decision about dose reduction and tolerability should be made according to the pre-specified criteria and the Investigator's clinical judgment.

If a subject is experiencing intolerance to study drug, they should first be conservatively managed using standard of care and maintain the starting dose of study drug (active or placebo).

If the subject continues to present significant intolerable AEs at the following scheduled or unscheduled visit and the Investigator deems it necessary, the daily dose of study drug can be reduced from 300 mg QD to 200 mg QD while tolerability is managed with standard of care.

If the subject continues to present significant intolerable AEs at the following scheduled or unscheduled visit and the Investigator deems it necessary, the dose of study drug can be reduced from 200 mg QD to 100 mg QD.

If the subject continues to present significant intolerable AEs at the decreased dose of 100 mg QD and the Investigator deems it necessary, the subject may discontinue study treatment.

All dose reductions during the Treatment Period will be done in 100 mg decrements. Dose reductions will be conducted via the Interactive Web-based Response System (IWRS).

Subjects who do not tolerate a minimum dose of 100 mg/day will be withdrawn from the study (Section 10.1.3.1 and Section 10.1.3.2).

Subjects with worsening scleroderma such as skin thickening or other scenarios will be allowed to use rescue therapy starting at or after Week 26, and those with confirmation of predicted FVC decline (after 2 separate confirmations within 4 weeks via an unscheduled visit) will be allowed to use rescue therapy starting at or after Week 16 (Section 11.3.1.2).

End of treatment (EOT) or early termination (ET) assessments will be performed for all subjects, who will undergo efficacy and safety evaluations. Efficacy evaluations will include change in

the composite score of ACR CRISS Components, [REDACTED], [REDACTED]
[REDACTED], and certain biomarkers.

[figure not shown]
Subjects who discontinue study treatment before EOT (Week 52) should be encouraged to continue in the study and complete all the required study assessments through Week 52.

If a subject decides to permanently withdraw consent from the study, every attempt should be made to have the subject complete the ET visit and complete the study assessments listed at Week 52 (Table 1).

In the event a subject does not return to the clinical site for the ET and/or safety follow-up visit, the Investigator must make every effort to contact the subject by telephone to for the collection and source documentation of safety information such as AEs, dosing compliance, and review of concomitant medications and date of last dose of study drug. Return of unused medication will be performed by courier where allowed.

A safety follow-up visit will occur at Week 56 (Visit 9) for subjects who complete the double-blind treatment period (Week 52) and 4 weeks after the last dose of study drug for subjects who ET from the study.

Further details can be found in the Study Schema (Figure 1).

a Starting daily dose will be MT-7117 300 mg QD or matching placebo, with possibility to reduce the dose in a stepwise manner from 300 mg QD to 200 mg QD and possibly from 200 mg QD to 100 mg QD to manage subjects' tolerability to study drug.

b At the discretion of the Investigator, rescue therapy may start as early as Week 16 with confirmation of predicted FVC decline, and as early as Week 26 with worsening scleroderma such as skin thickening or other scenarios.

Figure 1: Study Design Schema

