8.2.1 Risk/Benefit Assessment

8.2.1.1 Overall

MT-7117 is an investigational drug and its safety profile in humans has not yet been fully investigated. Therefore, all subjects will be closely monitored based on the completed clinical study safety observations/data. Results of the completed clinical studies conducted with MT-7117 so far, and the information of ongoing or planned studies with MT-7117 can be found in the IB.^{14,40}

In embryo-fetal development study in mice, the total incidence of fetuses with skeletal anomalies was increased at 500 mg/kg/day, the lethal dose for adult female mice, with increased incidence of fused rib and fused sternebrae.

In the rat pre- and postnatal development study (ongoing study), 2 dams died on lactation day (LD) 11 and LD 18 at 300 mg/kg/day. The causal relationship of these deaths to MT-7117-

treatment has not been established. In the F1 offspring, MT-7117 related toxicities were observed in the 300 mg/kg/day group: a total litter loss of 2 dams, a significant increase or tendency towards an increase in deaths and cannibalism, and lower body weights.

Female subjects of child-bearing potential and male subjects with partners of child-bearing potential participating in this study will be required to use effective contraception as defined in Appendix 3, and female subjects who are pregnant, lactating, or intending to become pregnant during the study are excluded from the study.

The Sponsor will undertake all reasonable measures, including thorough screening and safety monitoring procedures, to minimize the risk to subjects. Due to the potential of MT-7117 to increase liver function markers, LFTs will be monitored at all planned study visits and assessment of adverse events (AEs) related to elevation of liver function markers and liver injury will be conducted. Additionally, subjects will be instructed to immediately stop study treatment if they meet any of the withdrawal criteria listed in Section 9.5.

The risk-benefit relationship was carefully considered in the planning of the study. Based on the nonclinical and clinical data obtained so far, the conduct of this study is considered justifiable using the dose and dosage regimen of MT-7117 as specified in this clinical study protocol.

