9.5 Withdrawal from the Study and/or Treatment

A subject will be withdrawn from the study if ANY of the following criteria are met:

1. The subject requests to voluntarily withdraw from further participation in study.
2. The subject is significantly noncompliant with the protocol.
3. A female subject becomes pregnant while on the study.
4. Continuing in the study would be detrimental to the subject's safety in the opinion of the Investigator, for example:
 - a. The subject experiences intolerable AEs, SAEs, or adverse events of special interest (AESIs).
 - b. The subject has clinically significant changes in safety parameters at any of the postdose time points, as confirmed with a repeat assessment performed as soon as possible after the initial out-of-range result.
 - c. The subject experiences any clinically significant adverse findings from postbaseline nevi (Melanocytic Lesions) evaluation and adverse change is demonstrated histologically and confirmed by central pathologist. Visual evaluation of change will not be acceptable criteria for permanent discharge from treatment (Section 12.4).
 - d. Development of any clinically significant liver abnormalities defined as follows:

- ALT or AST $> 8 \times$ ULN.
- ALT or AST $> 5 \times$ ULN for more than 2 weeks.
- Elevated total bilirubin $> 2 \times$ ULN and ALT or AST $> 3 \times$ ULN or
- Symptoms consistent with liver dysfunction (e.g., fatigue, nausea, vomiting, abdominal pain or tenderness, fever, rash, eosinophilia $> 5\%$) with concomitant ALT or AST values $> 3 \times$ ULN.

Subjects meeting the laboratory criteria of ALT/AST and total bilirubin defined above (with or without alternative etiology), regardless of whether clinically significant or not, should be reported as a hepatic AESI (Section 14.3). The Investigator should discuss with the Sponsor Medical Monitor about the determination of etiology and the potential of interruption or withdrawal from study drug.

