10.1.3.2 Dose Reduction Criteria

Subjects will be informed regarding potential side effects. If the side effects experienced by subjects are not manageable through nonpharmacologic and pharmacologic treatment (using standard of care), dose reduction (from 300 mg QD to 200 mg QD, or from 200 mg QD to 100 mg QD) should be considered to manage the incidence and/or intensity of the subject-reported AEs (including but not limited to vomiting, diarrhea, headache, hyperpigmentation).

For safety reasons, the Investigator may also decide to implement a dose reduction for a subject. The following are criteria for Investigator initiated dose reduction:

- AEs which are classified as serious and/or moderate/severe (in severity), which did not improve with clinical management according to standard of care per Investigator's judgement, AND
- AEs assessed as having reasonable possibility of relationship to MT-7117 per Investigator's judgement (Section 14.5).

Examples of severe AEs include AE which limit self-care activities of daily living (independently eat, dress, walk/transfer from 1 position to another, bathe, toilet, maintaining bowel/bladder continence).

Note: Dose up-titration after dose reduction is not allowed.

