10.1.3.3 Dose Interruption

Dose interruption can be considered after the discussion with the Sponsor Medical Monitor in the case, such as

- 1) in subjects with suspicious lesions or change in nevi (Melanocytic Lesions) that had their dose temporarily interrupted can resume study treatment at the same dose they were interrupted at after the evaluations are complete and nevi (Melanocytic Lesions) and/or other lesions are determined to be benign; or
- 2) in a subject with an initial positive urine pregnancy test, awaiting a confirmatory test. If the confirmatory test is definitively negative, dosing may resume at the same dose they were interrupted; or
- 3) in a subject with any laboratory or clinical abnormality such as meeting the criteria of AESI (see Section 14.3 and 14.3.1), awaiting a confirmatory test and/or a judgement whether it is clinically significant. Resumption of dosing at the same dose they were interrupted will be considered based on the discussion with the Sponsor Medical Monitor and Investigator and should be closely followed up.

At any time during the study, subjects may be withdrawn from study treatment if continuing study treatment would be detrimental to the subject's safety in the opinion of the Investigator.

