Subjects who do not tolerate a minimum dose of [REDACTED] day will be withdrawn from the study.

Subjects with worsening scleroderma such as skin thickening or other scenarios will be allowed to use rescue therapy starting at or after Week 26, and those with confirmation

of predicted FVC decline (after 2 separate confirmations within 4 weeks via an unscheduled visit) will be allowed to use rescue therapy starting at or after Week 16.

End of treatment (EOT) or early termination (ET) assessments will be performed for all subjects, who will undergo efficacy and safety evaluations. Efficacy evaluations will include change in the composite score of ACR CRISS Components, PGIC, PGIS, UCLA SCTC GIT 2.0 questionnaire, PROMIS-29 test questionnaire, and certain biomarkers.

[figure not shown]
Subjects who discontinue study treatment before EOT (Week 52) should be encouraged to continue in the study and complete all the required study assessments through Week 52.

If a subject decides to permanently withdraw consent from the study, every attempt should be made to have the subject complete the ET visit and complete the study assessments listed at Week 52.

In the event a subject does not return to the clinical site for the ET and/or safety follow-up visit, the Investigator must make every effort to contact the subject by telephone to for the collection and source documentation of safety information such as AEs, dosing compliance, and review of concomitant medications and date of last dose of study drug. Return of unused medication will be performed by courier where allowed.

A safety follow-up visit will occur at Week 56 (Visit 9) for subjects who complete the double-blind treatment period (Week 52) and 4 weeks after the last dose of study drug for subjects who ET from the study.

Further details can be found in the Study Schema below.

- a) Starting daily dose will be MT-7117 [REDACTED] QD or matching placebo, with possibility to reduce the dose in a stepwise manner from [REDACTED] QD to [REDACTED] QD and possibly from [REDACTED] QD to [REDACTED] QD to manage subjects' tolerability to study drug.
- b) At the discretion of the Investigator, rescue therapy may start as early as Week 16 with confirmation of predicted FVC decline, and as early as Week 26 with worsening scleroderma such as skin thickening or other scenarios.

Figure 1 Study Design Schema

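### Protocol 8.1 both withdraws from the study and asks to keep to Week 52 the subjects who cannot tolerate 100 mg/day; a Week 52 ACR CRISS score lost this way is handled only under missing at random

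*Protocol*

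**What the plan says.** Three places give an unconditional order. Protocol 8.1 has "Subjects who do not tolerate a minimum dose of 100 mg/day will be withdrawn from the study"; the synopsis (Methodology) has the same sentence; and SAP 3.1 has it with the dose blacked out, ending "day will be withdrawn from the study".

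The same sections also say something else. Shortly before that sentence, Protocol 8.1 takes the subject who still has intolerable adverse events at 100 mg and says that, if the investigator finds it necessary, "the subject may discontinue study treatment". Further on it adds: "Subjects who discontinue study treatment before EOT (Week 52) should be encouraged to continue in the study". SAP 3.1 carries both statements. Protocol 9.5 likewise allows subjects off study drug to stay in the study and wants them followed to Week 52, there subject to the investigator's discretion.

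For the missing score, SAP 8.2.1 imputes Week 52 ACR CRISS by fully conditional specification under MAR, with 50 datasets. SAP 7.2 assigns the CRISS components to Week 52 only on Days 320 to 379.

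**The concern.** A site with a subject who fails at 100 mg cannot obey both instructions. If it takes the withdrawal sentence literally, the subject leaves and the Week 52 score is never observed, although the rest of the plan wants it collected. The subjects affected have all stopped for intolerance, so they are a group in which MAR deserves a test. If the drug works and those who stop do worse at Week 52 than the imputation predicts, the treatment effect is overstated, and no readable analysis would show by how much. Data lost in this way cannot be recovered later.

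**Working it through.** **1. Do the cited sections resolve the conflict?** The sentence in 8.1 refers to Protocol 10.1.3.1 and 10.1.3.2. The first describes the dose-reduction visit. The second ends at the step to 100 mg: "dose reduction (from 300 mg QD to 200 mg QD, or from 200 mg QD to 100 mg QD) should be considered". Neither says what follows failure at 100 mg. The next section, 10.1.3.3, speaks of treatment and not of the study: "subjects may be withdrawn from study treatment if continuing study treatment would be detrimental". The conflict stands.

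**2. When could the rule apply?** On scheduled visits alone, for a subject intolerant from the start: managed conservatively at Week 2, 200 mg at Week 6, 100 mg at Week 16, stop at Week 26 (Day 183). Unscheduled visits can bring this forward, and later onset moves it back.

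**3. What happens to the data?** An early-termination assessment at Day 183 falls in the Week 26 window (Days 148 to 228). The SAP 7.2 window table for the CRISS components has no early-termination row, and values from outside a window are not used to fill it. Week 52 CRISS is therefore missing. What counts is the date of the last assessment: one on or after Day 320 would still serve as Week 52.

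**4. Which primary-endpoint analyses test MAR?**
- Primary analysis: imputed under MAR.
- Analysis without post-rescue data: same method.
- Per-protocol analysis: requires completion of Week 52 (SAP 5.3), so these subjects drop out.
- Dose-level comparisons: run on the same imputed datasets.
- The one readable rule that departs from MAR counts missing as non-improvement. It belongs to the secondary improvement proportion (Protocol 16.3.4.2), which SAP section 10 removes.

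Part of the imputation text is redacted, so the statement is limited to what can be read.

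**5. The plan's own figure.** Protocol 16.1 gives 36 per arm, difference 0.35, SD 0.5, two-sided alpha 0.05 and 80% power for the Wilcoxon-Mann-Whitney test. By Noether's formula, P(X>Y) = Φ(0.7/√2) = 0.690, total N = (1.960 + 0.842)² / [3 × (0.690 − 0.5)²] = 72.7 (unrounded P), and power at 72 is 79.6%. A simulation on normal data gives 81.5%. The stated 80% reproduces.

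**6. Illustration of size.** Assume that k of 36 active subjects are lost, are placebo-like at Week 52, and are imputed like retained active subjects. The number k is an assumption. The difference with everyone counted as they truly are is 0.35 × (36 − k)/36, and the imputation targets 0.35, so the overstatement is 0.35 × k/36:

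| k | True difference | Overstatement |
|---|---|---|
| 1 | 0.340 | 0.010 |
| 2 | 0.331 | 0.019 |
| 4 | 0.311 | 0.039 |

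With no drug effect, 0 × k/36 = 0. If MAR holds, lost subjects are imputed correctly on average and the overstatement is again about zero. For scale, the standard error of a mean difference at the design SD is 0.5 × √(2/36) = 0.118, so the figure for four lost subjects is about a third of it.

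**7. Power.** If MAR holds and the imputation recovers nothing, power (normal approximation with Wilcoxon efficiency 3/π) is Φ(0.35 / {0.5 × √[1/((36 − k) × 3/π) + 1/(36 × 3/π)]} − 1.960). This is 82.7% at k = 0, 81.6% at k = 2 and 80.4% at k = 4. The power loss is small; the issue is possible bias.

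**The case against.** The best defence is that study withdrawal may be intended. Protocol 9.5 opens with "A subject will be withdrawn from the study if ANY of the following criteria are met", and item 4a names intolerable adverse events. That stands in part. However, item 4 applies only where the investigator judges that continuing in the study would harm the subject, and 4a is an example under that condition. It supports withdrawing some of these subjects. It does not support an order covering all of them.

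A reader might go further and infer that the protocol as a whole means treatment discontinuation, so that the 9.5 criteria should be rewritten too. For instance, 8.2.1.1 says "subjects will be instructed to immediately stop study treatment if they meet any of the withdrawal criteria listed in Section 9.5", and the pregnancy, nevus and liver text elsewhere also speaks of stopping treatment. This evidence does not decide the matter, because a subject withdrawn from the study also stops treatment. Rewriting item 4 would also encourage follow-up in subjects for whom staying is judged detrimental.

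Three further points stand. The rule is reached only after conservative management and failure at 300, 200 and 100 mg, so few subjects may be affected. CRISS scores from earlier visits, including an early-termination visit that falls in an earlier window, enter the imputation and soften the loss. And the request for an analysis outside MAR does not depend on this sentence; it would apply to any dropout. In a Phase 2 proof-of-concept trial it is good practice more than a necessity.

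**Conclusion.** The contradiction is real, appears in both documents, and is not resolved by the sections cited. Its consequence is limited to sites that follow the unconditional sentence with a last assessment before Day 320. The size cannot be fixed from the documents: about 0.010 per lost active subject on the mean scale, if such subjects are placebo-like and imputed as retained active subjects. This is an illustration and not a bound. The primary estimate is a Hodges-Lehmann shift, for which the figure can be smaller or larger.

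Two stronger readings are not supported. A reader might infer from Protocol 8.2.2, which reports more discontinuations for adverse events at 300 mg than at 100 mg or on placebo in an earlier trial, that this rule will drain the active arm. That comparison concerns 300 mg, with 100 mg as a comparator; it gives no rate for failure at 100 mg, and k could be zero. A reader might also infer a raised false-positive rate, but in this illustration the overstatement vanishes when the drug has no effect. The point merits a low-cost correction; it does not undermine the design.

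**What to change.** 1. In the synopsis and Protocol 8.1, change the sentence so that subjects who cannot tolerate 100 mg/day stop study treatment and, at the investigator's discretion, are encouraged to stay for the assessments up to Week 52. Make the same change in SAP 3.1 for consistency; sites do not work from that copy. Leave the withdrawal criteria in 9.5 and the unblinding rule in 13.6 as they are.

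2. In SAP 8.2.1, prespecify one sensitivity run of the existing 50-dataset imputation in which subjects who are off treatment and lack a Week 52 score are imputed from the placebo-arm model. A tipping-point shift would also serve.

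The cost is a few lines of wording, some visits by subjects off drug, one more analysis run, and a sensitivity result that may look less favourable. The SAP is to be finalised before database lock, so the second change can be prespecified until then even if the first comes too late for some subjects.
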